6.4 Statistical Analyses

Detailed analyses of the primary endpoints will be performed when all of the subjects complete their primary follow-up visit at 180 days. No effort will be made to impute or extrapolate data to replace missing values. All calculations will be based on available data with missing data excluded.

Analysis of Primary Endpoints

The primary safety endpoint of freedom from target lesion failure (TLF) rate at 6 months post-index procedure will be analyzed using the safety population.

The analysis of the primary effectiveness endpoint of LLL at 6 months will utilize the evaluable populations.

Analysis of Secondary Endpoints

All secondary endpoints will be analyzed using descriptive statistics.

For binary variables, such as technical success counts, percentages and exact 95% confidence intervals using Clopper-Pearson's method will be calculated. For continuous variables, means, standard deviations, and 95% confidence intervals for the mean using the Gaussian approximation will be calculated. If the assumption of normality seems untenable, nonparametric methods will be employed instead.

For time-to-event variables, such as time to target lesion revascularization, survival curves will be constructed using Kaplan-Meier estimates.

Analysis of Other Data

The clinical laboratory values collected will be analyzed by tabulating the number and percentage of subjects with clinically significant changes from baseline for each parameter at each time point.

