6.3 Sample Size Justification

Approximately 50 subjects at up to 15 active sites will be enrolled in the CVT-ISR Trial. All subjects will be scheduled for clinical examination at six (6) months. The objective of the study is to assess the initial feasibility and performance of the CVT Everolimus-Coated PTCA Catheter in the treatment of subjects presenting in-stent restenosis in coronary arteries. The study is powered (per PASS13) based on the primary safety and effectiveness endpoints.

The primary safety endpoint for this analysis is freedom from target lesion failure (TLF) rate at 6 months post-index procedure, defined as a composite rate of all cardiac death, target vessel myocardial infarction and clinically-driven target lesion revascularization (TLR). The null (H0) and alternative (HA) hypotheses are:

H₀: ffTLF historical control \leq ffTLF _{CVT} treatment

H_A: ffTLF_{historical control} > ffTLF_{CVT treatment}

The proposed sample size of N=50 is based on the primary safety endpoint of freedom from TLF rate at 6 months post-index procedure. The sample size calculation is based on the following assumptions:

- A single comparison of CVT Treatment group to a safety OPC of 65%.
 - $\circ~$ A positive safety endpoint result would be where the lower limit of the 90% CI exceeded the OPC=65%
 - One-tailed α =0.05

The safety focus will be to estimate the frequency of TLF at six (6) months postprocedure and the associated 90% confidence interval.

If 8 of 50 (16%) subjects experience TLF, the point estimate for ffTLF is 84% and corresponding the 90% CI is [73%, 92%], well above the OPC of 65%.

By enrolling 50 subjects there is 95% power to detect a 19%-point margin over the Safety OPC, with a one-tailed α =0.05.

The primary effectiveness endpoint is late lumen loss at six (6) months. The null (H_0) and alternative (H_A) hypotheses are:

H₀: Late Loss historical control ≤ Mean Late Loss CVT treatment

HA: Late Loss historical control > Mean Late Loss CVT treatment
The power calculation is based on the following assumptions:

- A single comparison of CVT Treatment group to an historical control group.
- A true mean difference between the historical control group and the treatment group of 0.50 mm. This assumption is made based on the results of historical studies. Assuming the true mean late loss for the CVT treatment group is 0.30 mm, the difference between the control group and treatment group is calculated as: 0.80 mm 0.30 mm = 0.50 mm.

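### On its natural reading, the missing-data rule drops subjects lost event-free before 6 months from the primary freedom-from-TLF rate, and no analysis shows how far the result depends on them

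*Combined protocol and SAP*

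**What the plan says.** Section 6.4 opens with two sentences that come before, and so govern, the primary analyses: "No effort will be made to impute or extrapolate data to replace missing values" and "All calculations will be based on available data with missing data excluded". It then assigns primary ffTLF to the safety population, which section 6.2 defines as all enrolled subjects in whom the procedure was initiated, with no follow-up requirement.

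Section 6.3 works the endpoint as a simple proportion: 8 failures in 50, a rate of 84%, a 90% CI of 73% to 92%. Success means a lower 90% limit above the objective performance criterion (OPC) of 65%. The power statement is "By enrolling 50 subjects there is 95% power to detect a 19%-point margin over the Safety OPC", at one-tailed alpha 0.05. The same 50 subjects are enrolled and analysed, with no allowance for loss.

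For time-to-event variables, under secondary endpoints only, section 6.4 says "survival curves will be constructed using Kaplan-Meier estimates".

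Section 3.11 foresees withdrawal and loss to follow-up, and declares loss only after two consecutive missed contacts. Section 4.6 places the post-discharge contacts at 30 ± 7 days and 180 ± 30 days, then at 12 months. No section says what makes a 6-month outcome complete, how a subject lost event-free before then is counted, or how sensitive the result is to such subjects.

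**The concern.** A failure is known as soon as it happens. Freedom from failure at 6 months is known only after follow-up to 6 months. A rule that uses only known outcomes therefore keeps early failures and discards event-free partial follow-up.

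The direction of the error depends on why subjects are lost. Loss unrelated to outcome makes the device look slightly worse than it is. Loss because of failure, for example a revascularization at another hospital, makes it look better. The second case matters more for a safety endpoint in a first-in-human study, and as planned the report would not reveal it.

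**Working it through.** **Inputs.** From section 6.3: N = 50, OPC 65%, assumed true rate 84%, one-sided alpha 0.05, success if the lower 90% limit exceeds 65%. The documents give no loss rate; 10% by 6 months is an assumption, with 5% and 20% as the range.

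**The plan's own figures.** The Clopper-Pearson 90% interval for 42/50 is 73.0% to 91.8%, matching the stated 73% to 92%. Power by the normal approximation is Φ[(0.19 − 1.645·√(0.65·0.35/50)) / √(0.84·0.16/50)] = 93.6%, near the stated 95%. The exact rule that goes with the stated interval passes at 39 or more event-free of 50: power 90.7%, one-sided error 3.4%. The comparisons below start from 90.7%.

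**Loss unrelated to outcome, spread over follow-up (10%).** With exponential times and 6 months as the unit, λ = −ln 0.84 = 0.1744 and μ = −ln 0.90 = 0.1054.
- Observed failures: λ/(λ+μ) · (1 − e^−(λ+μ)) = 0.6233 · 0.244 = 0.152
- Event-free and followed: 0.84 · 0.90 = 0.756
- Available-data rate: 0.756/(0.756 + 0.152) = 83.2 to 83.3%, a bias of about 0.8 points

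**Same loss, but lost subjects last seen at day 30.** Failures by day 30: 1 − 0.84^(30/180) = 0.0286. Observed failures: 0.90 · 0.16 + 0.10 · 0.0286 = 0.1469. Rate: 0.756/0.9029 = 83.7%, a bias of about 0.3 points.

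**Chance of passing at a true 84% (simulated trials of 50).**

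| Handling at 10% loss | Mean rate | Passes |
|---|---|---|
| No loss | 84.0% | 90.7% |
| Available data, loss spread | 83.2% | about 85% |
| Available data, last seen day 30 | 83.7% | about 87% |
| All lost subjects dropped, events included (smaller n only) | 84.0% | 87.6% |
| Kaplan-Meier, log-log 90% CI, loss spread | 84.0% | 90.1% |

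Smaller n alone costs 90.7 − 87.6 = 3.1 points. That is about half of the 6-point fall with spread loss and about three quarters of the 4-point fall with loss at day 30. With spread loss of 5% and 20%, the available-data rule passes 87.7% and 75.9%; Kaplan-Meier passes 91.2% and 87.8%. At a true 65% and 10% loss, Kaplan-Meier passes falsely about 4% of the time.

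**Loss because of failure.** Take 9 observed failures and 3 lost.
- Available data: 47 − 9 = 38, so 38/47 = 80.9%, lower limit 69.0%: passes
- If the 3 had failed: 38/50 = 76.0%, lower limit 64.0%: fails

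**At the planned 8 failures.**
- Available data with 5 lost: 37/45 = 82.2%, lower limit 70.2%
- Available data with 10 lost: 32/40 = 80.0%, lower limit 66.8%, still above 65%
- Lost counted as failures, 3 lost: 39/50, lower limit 66.2%, passes
- Lost counted as failures, 4 lost: 38/50, lower limit 64.0%, fails

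**The case against.** The strongest reply is that the plan never says lost subjects leave the denominator; a safety population of everyone treated points the other way. That stands: exclusion is an inference, though the natural one from the missing-data sentence. The alternative is no safer. Keeping lost subjects as event-free raises the mean to 84.8% at 10% loss and, at a true 65%, raises the false-pass rate from 3.4% to about 5.6%. Either reading needs a written rule.

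Second, the downward bias is small, and it is conservative for a safety endpoint. That also stands. A reader might infer that the rule simply makes the trial harder to pass. The documents do not support that, because the direction reverses when loss is related to failure.

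Third, cases where two losses flip the result lie at the boundary. Eleven failures is the most that passes with 50 counted (39/50, 66.2%), and dropping two event-free subjects then just fails (37/48, 64.9%). That is fair, and at the planned rate nothing so fragile occurs.

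Fourth, two tempting illustrations do not work. A subject seen event-free at day 150 is inside the 180 ± 30 day window. A non-cardiovascular death is not a TLF, and Appendix B classifies deaths by cause, so nothing makes that subject's status up to death unknown.

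Fifth, section 6.1 calls this a feasibility trial in which significance is neither necessary nor sufficient. That lowers the stakes of the pass rule, but the same section puts the emphasis on estimation, so how the estimate is formed still matters.

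**Conclusion.** The point holds as a worthwhile correction, not as a flaw that undermines the trial. Section 6.4 states a complete-case rule that, naturally read, handles primary ffTLF unevenly and gives no view of the opposite risk. With unrelated loss of an assumed 10%, the bias is 0.3 to 0.8 points, and the chance of passing drops from about 91% to 85-87%, half or more of it from smaller n. With loss due to failure the bias is upward, and a few subjects can change the result when failures run a little above plan.

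These sizes rest on assumed loss rates, exponential times and a true rate of 84%. The documents do not support a claim that subjects certainly will be dropped, that the result certainly will be pessimistic, or that the planned outcome is at risk: at 8 failures the OPC is met on available data with 10 lost.

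**What to change.** In section 6.4, for primary ffTLF:

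1. Estimate the 6-month rate by Kaplan-Meier in the full safety population. Censor event-free subjects at last contact, and at non-cardiovascular death. Report a 90% CI by the log-log method, or the exact Clopper-Pearson interval if nobody is lost before the visit window.
2. Treat an event-free subject followed to at least the start of the 180 ± 30 day window as having a 6-month outcome.
3. Add a sensitivity analysis that counts subjects with unknown 6-month status as TLF, with the exact 90% CI. Non-cardiovascular deaths are not counted as TLF.

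The cost is some wording and two extra lines of output; Kaplan-Meier is already in the plan and needs no imputation. The downsides are that the Kaplan-Meier interval is approximate at n = 50, that censoring at non-cardiovascular death sets aside a competing event and should be stated openly, and that the worst-case result may look less favourable.

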Other Clinical Endpoints	 Target lesion failure (TLF) at 30 days, 1, 2 and 3 years post-procedure, defined as a composite rate of cardiovascular death, target vessel myocardial infarction and clinically-driven target lesion revascularization (TLR). Target vessel failure (TVF) at 30 days, 180 days, and 1, 2 and 3 years post-procedure, defined as a composite rate of cardiovascular death, target vessel myocardial infarction, and target vessel revascularization (TVR). Clinically-driven target lesion revascularization (TLR) at 1, 2 and 3 years post-procedure. Clinically-driven target vessel revascularization (TVR) at 180 days and 1, 2 and 3 years post-procedure. Rate of vascular access site complication, defined as the combined rate of hematoma, AV fistula or a pseudoaneurysm that required intervention, such as surgical repair or transfusion, prolonged hospital stay or required a new hospital admission. Lesion success (per device), defined as achievement of a final in-lesion residual diameter stenosis of <30% (by QCA), using any device after wire 						

	passage through the lesion. Pre- and post-dilatation of the lesion with a
	non-study device is considered part of assigned device treatment.
	• Technical success (per device), defined as achievement of a final in-lesion residual diameter stenosis of <30% (by QCA), using the CVT Everolimus-coated PTCA Catheter without a device malfunction after wire passage through the lesion. Pre- and post-dilatation are considered part of assigned device treatment.
	• Clinical success (per subject) defined as technical success without the occurrence of major adverse cardiac events during the procedure.
	• Procedural success (per subject) defined as lesion success without the occurrence of major adverse cardiac events during the procedure.
Angiographic, IVUS	Angiographic endpoints (subset of 25 subjects):
and OCT Endpoints	• In-segment LLL at 180 days
	• In-stent and in-segment % diameter stenosis (%DS) at 180 days
	• In-stent and in-segment angiographic binary restenosis (ABR) rate at 180 days
	IVUS endpoint (subset of 15 subjects):
	• In-stent % volume obstruction (%VO) at 180 days
	OCT endpoints (subset of 10 subjects):
	• % of stent strut coverage at 180 days
Subject	Subjects with documented in-stent restenosis in native coronary arteries.
Population	
Treatment Strategy	• Treatment of a single in-stent restenosis coronary artery lesion with up to two (2) CVT Everolimus-coated PTCA Catheters.

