A subset of fifteen (15) subjects will complete an intravascular ultrasound (IVUS) examination at both the index procedure and at 6 months post-procedure, as per the IVUS core lab guidelines.

The 15 subjects undergoing IVUS examination will represent the first patients enrolled

into the study.

Note: The end of the procedure is defined as the time after a complete final angiogram has been performed and the last guidewire and catheter have been removed. In case the subject needs to return to the procedure room and a guiding catheter is reinserted for dilatation, this is considered a reintervention. Removal of the sheath(s) may be done at the Investigators discretion.

All catheters, including the CVT Everolimus-coated PTCA Catheter, should be delivered and deployed per their respective Instructions for Use (reference Appendix E for CVT Everolimus-coated PTCA Catheter IFU). All balloon inflations should be captured per the core laboratory guidelines.

Optical Coherence Tomography (OCT)

A subset of ten (10) subjects will complete optical coherence tomography (OCT) imaging at both the index procedure and at 6 months post-procedure, as per the OCT core lab guidelines.

The 10 subjects undergoing OCT examination will represent the first subjects enrolled into the study undergoing angiographic follow up and not undergoing IVUS examination.

Note: The end of the procedure is defined as the time after a complete final angiogram has been performed and the last guidewire and catheter have been removed. In case the subject needs to return to the procedure room and a guiding catheter is reinserted for dilatation, this is considered a reintervention. Removal of the sheath(s) may be done at the Investigators discretion.

All catheters, including the CVT Everolimus-coated PTCA Catheter, should be delivered and deployed per their respective Instructions for Use (reference Appendix E for CVT Everolimus-coated PTCA Catheter IFU). All balloon inflations should be captured per the angiographic core laboratory guidelines.

Criteria for Bail-Out or Alternative Procedures

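### The 95% intervals for continuous secondary endpoints rest on a Gaussian approximation at n = 10, 15 and 25; read literally, they cover about 92% to 94% (minor)

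*Combined protocol and SAP*

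**What the plan says.** Under its heading for secondary endpoints, Section 6.4 sets the rule for continuous variables: "95% confidence intervals for the mean using the Gaussian approximation will be calculated". The next sentence adds a fallback: "If the assumption of normality seems untenable, nonparametric methods will be employed instead". No formula is given, and neither a t distribution nor any other small-sample adjustment is mentioned. Binary endpoints in the same paragraph get exact Clopper-Pearson intervals.

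The protocol summary fixes the imaging subsets. The entries read "Angiographic endpoints (subset of 25 subjects", "IVUS endpoint (subset of 15 subjects" and "OCT endpoints (subset of 10 subjects" (each quote stops before the closing bracket). Section 4.3 repeats these sizes, for example "A subset of ten (10) subjects will complete optical coherence tomography (OCT) imaging".

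The continuous endpoints concerned, listed in Section 3.5, are:

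- in-segment late lumen loss (LLL) and in-stent and in-segment percent diameter stenosis, n = 25;
- in-stent percent volume obstruction, n = 15;
- percent strut coverage, n = 10.

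Section 6.4 also says that secondary endpoints are analysed descriptively, and that missing values are excluded and not imputed.

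**The concern.** A Gaussian interval for a mean uses the normal quantile and treats the standard deviation as known. Here the SD has to be estimated from at most 25 subjects, and from only 10 for OCT. The extra uncertainty from estimating it is ignored, so the interval is too narrow for its label, most of all in the smallest subset.

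What is at stake is how precise the imaging results appear. For IVUS and OCT, a mean with its interval is essentially all that the plan will report. Anyone using those figures to plan a later study would take the uncertainty to be somewhat smaller than it is. The plan takes care to use exact intervals for proportions, and a t interval would be the matching choice for means at no extra effort.

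**Working it through.** **Inputs**

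- Nominal level 95%, two-sided, so z = 1.960 (Section 6.4).
- SD: the sample SD. Section 6.4 plans to report "means, standard deviations, and 95% confidence intervals for the mean", and the plan gives no known SD for these endpoints.
- n = 25, 15 and 10 (protocol summary; Section 4.3).
- SD of 0.5 mm for LLL, used only to illustrate width (Section 6.3, stated there for the primary LLL).

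**Reproducing the plan's 95%**

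Mean ± 1.960 × σ/√n covers 95% if σ is known. It is not known here. With the sample SD s in place of σ and normal data, (mean − μ)/(s/√n) follows a t distribution with n − 1 degrees of freedom. Hence:

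- coverage of the literal interval = P(|t(n−1)| < 1.960);
- width of the t interval relative to it = t(0.975; n−1) / 1.960.

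| Subset | n | Coverage, literal interval | Error rate (nominal 5%) | t quantile | Width ratio |
|---|---|---|---|---|---|
| OCT | 10 | 91.8% | 8.2% | 2.262 | 1.154 |
| IVUS | 15 | 93.0% | 7.0% | 2.145 | 1.094 |
| Angiography | 25 | 93.8% | 6.2% | 2.064 | 1.053 |

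Simulation with 300,000 normal samples per n gave 91.8%, 93.0% and 93.9% for the literal interval, and 95.0%, 95.0% and 95.1% for the t interval. So 95% is obtained with a known SD or with the t quantile, but not with the normal quantile and an estimated SD.

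**Missing scans**

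The documents give no attrition rate. Assuming for illustration that two or three subjects are lost per subset, coverage of the literal interval is 90.9% at n = 8, 92.6% at n = 13 and 93.7% at n = 22.

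**Size on a measurement scale**

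With SD 0.5 mm and n = 25:

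- literal half-width: 1.960 × 0.5/√25 = 0.196 mm;
- t half-width: 2.064 × 0.5/√25 = 0.206 mm.

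The difference is 0.01 mm.

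**Does the fallback help?**

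Its trigger is doubt about normality. The coverages above are computed for exactly normal data, where the fallback would not be invoked, so it leaves the shortfall in place.

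**The case against.** The strongest reply is that the plan never writes down 1.96. Making the method conditional on normality is compatible with a normal-theory interval, whose usual form is the t interval. If that was meant, coverage for normal data is 95% and only the wording is loose. This stands: the shortfall depends on the literal reading, and the text does not exclude the other.

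The second reply is that the largest shortfall, at n = 10, concerns one endpoint, strut coverage. That is a percentage bounded at 100 and an obvious candidate for the nonparametric route. This also stands in part. The 91.8% is exact only for normal data, and a t interval does not guarantee 95% for markedly skewed data. It does not rescue the rule for the endpoints where normality is acceptable.

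The third reply is that the effect is small and nothing is decided on these intervals. That is right, and it sets the severity.

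Two stronger readings may tempt a reader:

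- **The trial's main estimates are affected.** Section 6.1 does put the focus on estimating 180-day values with confidence intervals, but it specifies 90% intervals. The Gaussian sentence concerns 95% intervals for secondary endpoints.
- **The 90% interval for the primary LLL also under-covers.** The plan does not assign the Gaussian method to it. In Section 6.4 the paragraph on primary endpoints names analysis populations only, and no interval method for mean LLL is stated. An error in that interval cannot be claimed from the text.

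**Conclusion.** The point holds as a minor one. Read literally, the stated method gives nominal 95% intervals that cover 91.8%, 93.0% and 93.8% at n = 10, 15 and 25, a loss of 3.2, 2.0 and 1.2 percentage points, and slightly more if scans are missing.

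This rests on three assumptions:

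- the Gaussian approximation means the normal quantile with the sample SD;
- the data are normal;
- the secondary endpoints of Section 6.4 include the imaging endpoints of Section 3.5, which are not given that label where they are listed.

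No test, performance criterion or success rule is affected. The conclusion does not extend to binary restenosis, which has an exact interval, or to the primary LLL.

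**What to change.** In Section 6.4, replace the reference to the Gaussian approximation with the t distribution with n − 1 degrees of freedom, where n is the number of subjects analysed for that endpoint. Keep the nonparametric fallback. If a confidence interval for mean primary LLL is reported, it would be sensible to name the same t method for it; that is a clarification, not the correction of an error.

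The cost is one phrase, with no new data, subjects or procedures. Compared with the literal reading, intervals become about 15%, 9% and 5% wider at n = 10, 15 and 25. The change is best made before the 180-day data are analysed.

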4.1 Baseline Assessments

Subject preparation will occur in accordance with standard hospital policy for the care of interventional endovascular subjects. Baseline assessments will be documented in the subject medical record and on the case report form (CRF) as appropriate.

Subject History

Subject history will include but not be limited to the following risk factors and comorbidities: age, height, weight, body mass index (BMI), gender, hypertension, hyperlipidemia, diabetes mellitus, smoking, ischemic heart disease (history of myocardial infarction, angina pectoris, previous percutaneous or surgical coronary revascularization), history of peripheral vascular disease (previous percutaneous or surgical revascularization), deep vein thrombosis, congestive heart failure, renal insufficiency, renal disease, liver disease, cerebrovascular disease (known carotid artery disease, history of minor or major stroke or transient ischemic attack), and chronic obstructive pulmonary disease (COPD).

Medication History

A medication history should be documented which includes chronic concomitant medications and protocol required medications.

Clinical Assessments

A physical examination should be documented. The exam will include heart rate, blood pressure and body temperature.

Laboratory Assessments

A pregnancy test should be administered to all female subjects of childbearing potential within 14 days prior to the procedure.

The following laboratory tests should be obtained for all subjects within 7 days prior to the index procedure.

- Complete Blood Count
- Creatinine
- Absolute Platelet Count
- Coagulation tests as per standard of care of the hospital (e.g., Prothrombin Time (PT) and activated Prothrombin Time (aPTT).

The following laboratory tests should be obtained for all subjects within 72 hours of the index procedure.

- CK and/or CK-MB and cardiac troponin (cTn)
- 12 lead ECG.

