4.5 Pre-Discharge Assessments

Medication History

The medication history should be updated as needed to include modifications to the chronic concomitant medications and protocol required medications.

Laboratory Tests

- Complete Blood Count
- Absolute Platelet Count
- Coagulation tests as per standard of care of the hospital (e.g., Prothrombin Time (PT) and activated Prothrombin Time (aPTT).

Cardiac Tests

- CK and/or CK-MB and cardiac troponin (cTn)
- 12 lead ECG

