5.2 Anticipated Adverse Events

An anticipated adverse event is any untoward medical occurrence in a subject that is predefined in the protocol and/or Instruction for Use (IFU) and that is identified or worsens during a clinical study, regardless whether or not the event is considered related to the study device or drug regimen prescribed as part of the protocol.

The following is a list of adverse events that may result from the PTCA procedure.

- Acute myocardial Infarction (Cardiac)
- Aneurysm
- Arrhythmias, including ventricular fibrillation (bradycardia & tachycardia)
- Arterial Dissection
- Arteriovenous fistula
- Bleeding
- Coronary artery spasm
- Coronary artery thrombosis
- Death (Cardiovascular or non-cardiovascular related)
- Discomfort during procedure

- Drug reactions or allergic reactions to contrast medium
- Distal Embolism (air, thrombus, plaque)/Device Embolism
- Endocarditis
- Fever
- Groin bruising/discomfort
- Hematoma
- Hemorrhage
- Hypotension/hypertension
- Injury at blood vessel access site requiring surgical or medical treatment
- Ischemia
- Pseudoaneurysm
- Renal failure
- Restenosis of the dilated vessel
- Sepsis, infection
- Stroke or cerebrovascular event
- Total occlusion of the coronary artery or bypass graft
- Unstable angina
- Vessel dissection, perforation, rupture or injury
- Thrombosis
- Vomiting/Nausea

The oral formulation of everolimus has been evaluated in clinical trials and is approved worldwide for the prophylaxis of organ rejection in adult kidney transplant recipients at low-moderate immunologic risk and for the treatment of patients with advanced renal cell carcinoma. Oral dose of everolimus depending on the indication ranges between 1.5 and 20 mg/day. The following list includes the known risks of everolimus at these oral doses. *The following is a list of theoretical adverse events that may result from the addition of everolimus to a PTCA catheter:*

- Abdominal pain
- Anemia
- Angioedema
- Anorexia
- Asthenia
- Constipation
- Cough
- Delayed wound healing/fluid accumulation
- Diarrhea
- Dyslipidemia (including hyperlipidemia and hypercholesterolemia)
- Dyspnea
- Dysgeusia
- Dyspepsia

- Dysuria
- Dry skin
- Edema (peripheral)
- Epistaxis
- Fatigue
- Headache
- Hematuria
- Hyperglycemia
- Hyperlipidemia
- Hyperkalemia
- Hypertension
- Hypokalemia
- Hypomagnesemia
- Hypophosphatemia
- Increased serum creatinine
- Infections and serious infections: bacterial, viral, fungal, and protozoal infections
- Insomnia

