# CVT ISR Trial FIH Trial Protocol Number: TP1125 Case Report Forms

Г

Site ID		Subject Number Birth Year						
Pre-Procedure Laboratory Blood Values								
1. Is the subject female and of childbearing potential? $\Box$ YES $\Box$ NO $\Box$ NA (if N								
	1.1.	If yes, sample date of pregnancy test:						
	1.2.	Result of pregnancy test: $\Box$ Postive $\Box$ Negative $\Box$ Not Done						

Blood Test Sample Date:	
DD MM YYYY	

_			Range		Clinically Significant		Comment	
Parameter	Result	Unit	IN	O High	UT Low	(if out o Yes	of range) No	or Not Done
WBC								□ Not Done
Differential WBC								
Eosinophils								□ Not Done
Basophils								□ Not Done
Neutrophils								□ Not Done
Monocytes								□ Not Done
Lymphocytes								□ Not Done
Hemoglobin								□ Not Done
Hematocrit								□ Not Done
Absolute Platelet Count								□ Not Done
Serum Creatinine								□ Not Done
Prothrombin Time								□ Not Done
Activated Prothrombin Time								□ Not Done
Site ID	Subject Number	Birth Year						
---------	----------------	------------						
---------	----------------	------------						

CK and/or CK-MB cardiac Troponin

 $\hfill\square$  Not done.

Cardiac Enzymes	Date of Test: (dd/mm/yyyy)	Time (24 hour clock)	Value (U/L)	Upper Normal Limit (U/L)
СК	//	:		
CK-MB	//	:		
Troponin	//	:		

Site	e ID Subjec	t Number	Birth Year
	Antiplatelet and A	Anticoagulant Me	dication
1. 2.	Was Aspirin Administered Was an Antiplatelet Administered	□ YES □ □ YES □	NO NO
3.	What anticoagulant was administered	:	
4.	Was a glycoprotein (GP) IIb/IIIa recep	ptor blocker used: 🗆 Y	YES $\Box$ NO

Site ID	Subject Number	Birth Year
Target Lesion Treatment D	Procedural Form CB # 1 □ DCB # 2 □	

 
What was the location         
 
□ Femoral □ F
 
 
 
Arterial sheath size □
 
	of vascular access Radial □ Brachial 5F □ 6F □ 7F □ 8F	

 
3. ISR Stent Location
 
Right Coronary Artery
 
Proximal      Mid      Distal
 
Right Post. Descending
 
	
 
□ Left Anterior Descending
 
□ Proximal □ Mid □ Distal
 
□ Diagonal branch
 
	
 
□ Circumflex.
 
□ Proximal □ Mid □ Distal
 
□ Obtuse Marginal
 

4. Type of stent with ISR	$: \square BMS \square DES Sirolimus \square DES$	Everolimus 🗆 DES Paclitaxel
	□ DES Zotarolimus □ DES other	drug Specify

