#### **Blood Assessment**

1.	Were blood labs taken post-procedure and pre-discharge? $\Box$ YES	$\square$ NO
	If yes, complete the Laboratory Blood Values Form.	

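### No creatinine is scheduled after the procedure, so the laboratory change-from-baseline table in section 6.4 has no planned creatinine data for a renal risk that the protocol itself lists.

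*Combined protocol and SAP*

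**What the plan says.** The analysis text is the last paragraph of section 6.4, on other data. It takes the laboratory values that are collected and counts, with percentages, the subjects who show "clinically significant changes from baseline for each parameter at each time point". The same section rules out imputation and bases all calculations on available data.

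The measurement text is in three places.

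- Section 4.1 sets the baseline sample: "The following laboratory tests should be obtained for all subjects within 7 days prior to the index procedure". Creatinine is on that list with blood count, platelets and coagulation. CK and/or CK-MB and troponin are taken within 72 hours of the procedure.
- Section 4.5 lists the pre-discharge tests: blood count, platelets, "Coagulation tests as per standard of care of the hospital", and the cardiac markers. Creatinine is not among them.
- Section 4.6 schedules no laboratory test at 30 days or at 6, 12, 24 or 36 months. Table 3 and its copy in Appendix F agree and mark creatinine once, before the procedure.

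Section 5.2 lists renal failure among the events that may follow the PTCA procedure, and "Increased serum creatinine" among the theoretical events from adding everolimus to the catheter. Sections 7.1 and 7.2 name both again.

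In Appendix L, the post-procedure Blood Assessment page asks whether blood was taken before discharge and tells the site to "complete the Laboratory Blood Values Form". The only laboratory form shown is headed for pre-procedure values. It has a row for "Serum Creatinine" with a box for a test not done.

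**The concern.** The analysis plan and the sampling schedule do not meet for this one analyte. A change from baseline needs a second value, and none is planned. Section 9.6 describes the trial as first-in-human, and the missing analyte is the one that corresponds directly to the renal risks in section 5.2.

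Two consequences follow. First, the final table will either omit creatinine or fill its row from whichever sites happened to test. The second outcome is plausible, because the case report form offers a creatinine field that the schedule does not call for. Second, renal safety would then rest on adverse event reporting. Section 5.1 relies on spontaneous reports and general questioning, which will not reveal a creatinine rise without symptoms.

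**Working it through.** The plan gives no figure to reproduce on this point. The check is a count of scheduled samples per analyte, taken from sections 4.1, 4.5 and 4.6 and confirmed in Table 3 and Appendix F.

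| Test | Before procedure | Pre-discharge | 30 days to 3 years |
|---|---|---|---|
| Creatinine | 1 | 0 | 0 |
| Blood count and platelets | 1 | 1 | 0 |
| Coagulation | 1 | 1 | 0 |
| CK-MB | 1 | 1 | 0 |
| Cardiac troponin | 1 | 1 | 0 |

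**Subjects with a scheduled change value.** A subject contributes only with one value before and at least one after. With 50 enrolled:

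- Creatinine: 50 × 0 post-procedure samples = 0 subjects.
- Each other analyte: 50 × 1 = 50 subjects, if every scheduled sample is taken.

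Apart from the pregnancy test, creatinine is the only baseline blood test that is not repeated.

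**Time points.** After the procedure the schedule has six: pre-discharge, 30 days, 180 days, and 1, 2 and 3 years. Laboratory tests are marked at 1 of the 6. The one addition elsewhere is conditional: section 4.4 requires blood counts in subjects who receive ticlopidine. For every analyte, then, the reference in section 6.4 to each time point amounts to pre-discharge alone.

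**180-day angiogram.** The 25 subjects in the imaging subset return for angiography. Creatinine samples scheduled around that visit: 0.

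**What a full denominator would give.** If all 50 had a pre-discharge creatinine and none showed a significant rise, the one-sided 95% upper limit for the true rate would be 1 − 0.05^(1/50) = 0.058, or about 5.8%. With no scheduled samples, no limit can be stated.

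**The case against.** The best defence is that section 6.4 covers only the laboratory values that are collected, so it does not itself commit the trial to a second creatinine. The sampling sections are also consistent with one another. The baseline creatinine has an evident purpose of its own, because exclusion criterion 6 requires a value in the same 7-day window. On this reading creatinine is an eligibility test and section 6.4 is merely worded loosely. Laboratory values are also secondary material on which no hypothesis depends.

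Much of this stands. It means that section 6.4 is imprecise, not that a stated commitment is broken. It does not explain why a risk named in sections 5.2, 7.1 and 7.2 has no planned follow-up value when every other baseline blood test does.

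A reader might infer three stronger things that the documents do not support.

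- *That renal harm cannot be detected at all.* The adverse event definition in section 5.1 includes laboratory findings, and collection runs from device entry to 3 years. Renal failure, or a rise found in routine care, would be reportable. What is missing is systematic measurement.
- *That contrast is a documented renal hazard which the plan ignores.* For contrast, section 5.2 names drug or allergic reactions only, and its list for follow-up angiography does not include renal failure.
- *That a creatinine rise from the device is expected.* The everolimus list is called theoretical and derives from oral dosing. Section 7.2 considers such effects unlikely at the amount on the catheter.

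The form evidence also has a limit. Appendix L warns that its version may not be current, and a separate post-procedure laboratory form may exist.

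**Conclusion.** The point holds as a gap between the planned analysis and the sampling schedule. On scheduled data, creatinine change is available for 0 of 50 subjects, against up to 50 for each other baseline blood test. Renal harm would be seen only through adverse event reports or unscheduled tests. Neither gives a known number of subjects tested, so neither gives a rate.

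This rests on reading sections 4.1, 4.5 and 4.6 and both schedule tables as complete. They agree with one another, so a transcription slip in one table is an unlikely explanation. It needs no assumption about how often creatinine would rise, and the documents supply no such rate.

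The consequence is moderate. No primary endpoint, hypothesis or sample size depends on it. It deserves correction because the protocol names the risk, the study is first-in-human and the remedy is small.

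**What to change.** 1. Add creatinine to the pre-discharge laboratory list in section 4.5 and to the pre-discharge column of Table 3 and Appendix F.
2. In Appendix L, make clear which form the Blood Assessment page refers to, and confirm that the form has a creatinine row for the pre-discharge sample.
3. In section 6.4, replace the reference to each time point with the pre-discharge time point, and report for each analyte the number of subjects with both values.

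The cost is one more analyte on a sample already scheduled, one mark in each schedule table, and a few more laboratory findings for investigators to assess.

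The change has limits that should be stated. A pre-discharge value describes only the hospital stay. A single-arm study cannot attribute a rise to the drug, the procedure or anything else. The 25 subjects with a 180-day angiogram would still have no creatinine around that visit.

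Stating in section 6.4 that no creatinine change will be reported would remove the inconsistency, but it would leave the listed renal risk without a denominator. It is not an adequate substitute on its own.
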